3.8.2. Analysis Visit Windows

Participant visits might not occur on protocol-specified days. Therefore, for the purposes of analysis, observations will be assigned to analysis windows. The study day as defined in Section [3.8.1](#) will be used when data are summarized by visit.

Vital signs were to be collected daily; therefore, windows are not assigned, and results will be summarized for each Study Day, except for Study Day 28. For Study Day 28, the nominal day is Study Day 28, the lower limit is Study Day 15 and there is no upper limit.

Ordinal scale results were to be recorded prior to dosing on Study Day 1. The worst result for each day from Day 1 (after first dose) through the earliest of discharge date or Day 14 was to be recorded. For participants who were discharged after Day 14, changes in score category were to be recorded each day from Day 15 to the earliest of discharge date or Day 28. For the ordinal scale, baseline is defined as the value recorded prior to dosing, or the last value obtained prior to the first dose date if the predose value was not recorded on the day of dosing. Results will be summarized for each Study Day without windows. If more than one result was reported on the same day, the worst result will be selected.

The analysis windows for hematology and chemistry laboratory parameters are presented in [Table 3-1](#).

Table 3-1. Analysis Windows for Hematology and Chemistry Laboratory Tests (hemoglobin, hematocrit, platelet count, WBC, ALT, AST, total bilirubin, glucose, serum creatinine, and creatinine clearance)

Visit ID	Nominal Day	Lower Limit	Upper Limit
Baseline	1		1 (predose)*
Day 3	3	1 (postdose)*	3
Day 5	5	4	6
Day 8	8	7	8
Day 10	10	9	11
Day 14	14	12	15
Post Day 14**	28	16	

* For Baseline, the upper limit includes values collected at or prior to the first dose date/time. For Day 3, the lower limit includes values collected after the first dose date/time on Day 1.

** Post Day 14 laboratory values will be considered for treatment emergent laboratory presentations only.

3.8.3. Selection of Data in the Event of Multiple Records for an Analysis Visit Day

Depending on the statistical analysis method, single values may be required for each Study Day or analysis window. For example, change from baseline by visit usually requires a single value, whereas a time-to-event analysis does not require 1 value per Study Day or analysis window.

If multiple valid, nonmissing measurements exist for a Study Day/analysis window, records will be chosen based on the following rules if a single value is needed:

- For baseline, the last nonmissing value on or prior to the first dosing date (and time, if available) of study drug will be selected, unless specified differently. If there are multiple records with the same time or no time recorded on the same day, the baseline value will be the average of the measurements for continuous data, or the measurement with the lowest severity for categorical data.

- For postbaseline values:

For windows spanning multiple days, the record(s) collected on the day closest to the nominal day will be selected. If there are 2 days equidistant from the nominal day, the later day will be selected.

- For laboratory values and SpO₂ and partial pressure of oxygen, arterial (PaO₂), if there is more than 1 record on the selected day, the worst value will be selected. See [Appendix 2](#) for definition of worst value.
- For other parameters, if there is more than 1 record on the selected day, the average will be taken for continuous data and the worst severity will be taken for categorical data, unless otherwise specified.

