6.5. Day 28 Follow up Assessment (±5 Days)

The following evaluations are to be completed if this visit is conducted in person. For participants who have been discharged from hospital, the final evaluation can be made by phone. Only AE and concomitant medication and ordinal scale (if discharged on or after Day 14) review are to be completed if visit is conducted by phone.

- Physical examination and vital signs (heart rate, temperature, blood pressure)

- Documentation of respiratory status:

Respiratory rate

- Oxygen supplementation: room air, low flow O₂ (L/min and %), high flow O₂ (L/min and %), CPAP/BIPAP (FiO₂ or %), mechanical ventilation (FiO₂ or %), ECMO

Oxygenation: SpO₂ or PaO₂

Radiographic findings (if available)

- Review AEs and document concomitant medications
- Review the Ordinal Scale (Section 6.9). If subject was not discharged by Day 14, any change in category and the date of any change in category from Day 14 to discharge (or Day 28) should be recorded

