6.2. Efficacy Endpoints of Interest

Efficacy endpoints of interest include endpoints based on clinical status assessed by a 7-point ordinal scale. The endpoint will be derived by combining the available death, hospital discharge alive and ordinal scale assessment reported by the site, where death supersedes discharge alive and discharge alive supersedes the ordinal scale score reported by the site.

Sites were instructed to report the worst ordinal scale category for each day. Therefore, the ordinal scale result on the day the participant was discharged alive does not necessarily reflect Not hospitalized (7). The definition of clinical status based on the 7-point ordinal scale is defined as follows:

- If a participant dies while hospitalized (as recorded on the Death eCRF and Hospitalization eCRF), the endpoint on the day of death and all subsequent days through Day 28 will be set to Death (1)
- If the participant is discharged alive, the endpoint on the day of discharge alive and all subsequent days through Day 28 will be set to Not hospitalized (7)
- If the participant is discharged alive and dies on the same day or a later day (as recorded on the Death eCRF and Hospitalization eCRF), the endpoint on the day of discharge alive and all subsequent days until the day of death will be set to Not hospitalized (7). On the day of death and all subsequent days through Day 28, the endpoint will be set to Death (1),

Every effort will be made to obtain clinical status data for all participants prior to discharge alive. The last known clinical status will be used for days with missing clinical status (eg, where the reason for Hospital Discharge is not “Discharged Alive” and the participant has not died). All post-baseline days with missing ordinal scale score, from Day 2 to Day 14 and Day 28, will use the previous last known clinical status.

Efficacy endpoints of interest include

- Clinical status on Days 1 to 14, Day 28 and last available assessment
- Change in clinical status on Days 5, 7, 11, 14, 28, and last available assessment
- Time to clinical improvement (days): Clinical improvement is defined as a ≥ 2 -point improvement from baseline clinical status or discharged alive on the 7-point ordinal scale using the definition specified above.

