6.2.1. Analysis of Efficacy Endpoints of Interest

The number and percentage of participants in each clinical status category for each day from Baseline through Day 14 and at Day 28 and using the last available assessment will be summarized by group. These results will be summarized using (1) the clinical status definition in Section 6.2 and (2) with the definition specified in Section 6.2 but excluding days with missing ordinal scale score not due to death or discharge alive. In addition, stacked bar charts by study day (Baseline through Day 14 and at Day 28) will be produced by group using the definition specified in Section 6.2.

The number and percentage of participants in each clinical status category for each day from Baseline through Day 14 and at Day 28 and last available assessment will be summarized within each subgroup defined in Section 3.4.1.

The change from baseline in clinical status category on Days 5, 7, 11, 14, 28 and last available assessment will be summarized by group using descriptive statistics.

Number of days of oxygen support status modes (invasive mechanical ventilation, high flow oxygen, low flow oxygen) will be calculated as the number of days oxygen support was reported on the 7-point ordinal scale eCRF through death, discharge alive, or Day 14 and presented for each group using descriptive statistics.

A shift table of baseline oxygen support status (death, invasive mechanical ventilation, high flow oxygen, low flow oxygen, room air, discharge alive) to Days 5, 7, 11, 14, 28 and the last available status will be provided for each group.

Duration of hospitalization will be calculated only for participants who are discharged alive on or prior to Day 28 and will be summarized for each group using descriptive statistics.

All-cause mortality will be estimated for each group using the Kaplan-Meier product limit method with all available data. Participants who did not die will be censored at the last study day.

Days to clinical improvement and days to recovery will be estimated for each group using a competing risk analysis approach, with death as the competing risk. Participants without recovery will be censored on the day of the last non-missing ordinal scale assessment.

Forest plots by subgroup will be presented for all-cause mortality Kaplan-Meier estimates on Day 28 and cumulative incidence of recovery on Day 28.

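### With no Day 28 window for the ordinal scale, the observed-only Day 28 clinical status table can drop continuing inpatients and so inflates both the discharge and the death percentages

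*SAP*

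**What the plan says.** SAP 3.8.2 handles Day 28 differently for two measures collected daily. For vital signs it sets a window: "For Study Day 28, the nominal day is Study Day 28, the lower limit is Study Day 15 and there is no upper limit". For the ordinal scale it sets none: "Results will be summarized for each Study Day without windows".

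The protocol heads the follow-up section "6.5. Day 28 Follow up Assessment (±5 Days", so a compliant visit may fall on any of Days 23 to 33. The ordinal scale is reviewed at that visit. For participants not discharged by Day 14, the protocol adds that "any change in category and the date of any change in category from Day 14 to discharge (or Day 28) should be recorded". SAP 3.8.2 describes the same period in similar terms: "changes in score category were to be recorded each day from Day 15 to the earliest of discharge date or Day 28".

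SAP 6.2 builds clinical status from deaths, live discharges and site scores. After a live discharge, "the endpoint on the day of discharge alive and all subsequent days through Day 28 will be set to Not hospitalized (7"), and deaths are likewise set to category 1 through Day 28. Neither needs a score. Other missing scores, "from Day 2 to Day 14 and Day 28, will use the previous last known clinical status".

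SAP 6.2.1 then presents the category table in two versions: (1) under the Section 6.2 definition, and (2) under the same definition but "excluding days with missing ordinal scale score not due to death or discharge alive".

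**The concern.** In version (2) at Day 28, whether a participant can be excluded depends on the outcome. The dead and the discharged always have a status. A continuing inpatient has one only if a score carries the date of Study Day 28. Someone in a stable category who is seen on Day 26 or Day 30 has no such record, and neither does someone whose last change was on Day 20.

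Part B is descriptive, so its tables are its result. Version (2) is the only alternative to carry-forward that the SAP shows for clinical status. A reader who sees the two versions differ at Day 28 would naturally put it down to carry-forward, when the cause may be no more than the date of the visit.

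**Working it through.** **Plan's own figures.** The documents give no figure for the Day 28 table. Their only power statement (Part A, 400 participants, odds ratio 1.75, more than 85%) reproduces at 86.5% with the stated formula. It has no bearing on this point.

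**Who can be dropped from version (2) at Day 28**

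| Status at Day 28 | Score dated Day 28 needed? | Can be dropped? |
|---|---|---|
| Died | No (SAP 6.2) | No |
| Discharged alive | No (SAP 6.2) | No |
| In hospital, categories 2 to 6 | Yes (SAP 3.8.2, no window) | Yes |
| Neither dead nor discharged alive, status unknown | Yes | Yes, and rightly |

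**Formula.** Let d, h and v be the true shares dead, in hospital and discharged (d + h + v = 1). Let m be the fraction of inpatients with no score dated Day 28. The dropped fraction is h × m, so version (2) shows:

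- discharged: v / (1 - h × m)
- dead: d / (1 - h × m)
- in hospital: h(1 - m) / (1 - h × m)

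Discharge and death are multiplied by the same factor.

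**Inputs.** The documents give neither the Day 28 mix nor m. All values below are assumptions.

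*Mix A: 35% discharged, 30% dead, 35% in hospital.*

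- m = 0.25: denominator 1 - 0.35 × 0.25 = 0.9125. Discharged 0.35/0.9125 = 38.4%; dead 0.30/0.9125 = 32.9%; in hospital 0.2625/0.9125 = 28.8%.
- m = 0.50: denominator 1 - 0.35 × 0.50 = 0.825. Discharged 42.4%; dead 36.4%; in hospital 0.175/0.825 = 21.2%.

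*Mix B: 75% discharged, 10% dead, 15% in hospital.*

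- m = 0.25: denominator 0.9625. Discharged 77.9%; dead 10.4%.
- m = 0.50: denominator 0.925. Discharged 81.1%; dead 10.8%.

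**Ceiling.** If every inpatient lacked a Day 28 score (m = 1), the factor would be 1/(1 - h): 1.18 with 15% in hospital and 1.54 with 35%. The distortion grows with the share still in hospital. It would be larger in the Mechanically Ventilated Group if more of that group remain inpatients at Day 28, which is plausible but not stated.

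**Which outputs are touched.** SAP 6.2 defines the recovery, ≥1-point and ≥2-point percentages on the carry-forward status. The exclusion in version (2) is stated only for the category table. The stacked bar charts also use the Section 6.2 definition.

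**The case against.** The strongest reply is that a dated change log makes no change a known status. The SAP does not say that an inpatient without a new entry has a missing score. Its one example of missing status is a participant whose discharge reason is something other than alive and who has not died. The eCRF, which is not among the documents, may resolve this. That is fair as far as it goes. But the SAP does not state that reading either, and a rule that works by exact Study Day leads a programmer to the other one.

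The protocol also requires an ordinal review at the Day 28 visit, so some inpatients will have a score on the day. This stands, and it means that the number dropped cannot be derived from the documents.

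The contrast with vital signs is weaker than it looks, because the ordinal scale has a carry-forward rule that does much of a window's work in version (1). Nor does the SAP call version (2) a sensitivity analysis. Both remarks are right, but neither removes the outcome-dependent exclusion from version (2).

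Three stronger readings are tempting, and the documents do not support them:

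- **That recovery is overstated.** The recovery percentages keep these participants. Moreover, category 6 counts as recovery from a baseline of 2 to 5 but is an inpatient category, so the figures above describe discharge, not recovery.
- **That the bias favours the drug.** Death is inflated by the same factor as discharge.
- **That those dropped are mainly unchanged inpatients, or nearly all inpatients.** If visits were spread evenly over the 11 days, m would be 10/11 and, in mix A, discharge would read 51.3% and death 44.0%. Nothing in the documents supports an even spread, least of all for patients already in hospital.

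**Conclusion.** The point holds for one output: the observed-only clinical status table at Day 28, and the same table's inpatient categories. As written, it can lose continuing inpatients but never the dead or the discharged, so categories 2 to 6 are under-represented and both extremes are overstated.

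Under mix A, with a quarter to a half of inpatients unscored on the day, the overstatement is 3.4 to 7.4 percentage points for discharge and 2.9 to 6.4 for death. Under mix B it is 2.9 to 6.1 points for discharge and below 1 point for death. These sizes rest wholly on the assumed mixes and missing fractions.

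No test or error rate is affected, because Part B has no formal testing. Version (1) keeps all these participants, although without a window a score from Days 29 to 33 is not used there and an older status is carried forward instead. The time-to-event estimates have their own censoring rule and are not covered by this point.

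**What to change.** Add to SAP 3.8.2 and 6.2.1, for version (2) at Day 28:

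1. A participant confirmed as still hospitalized through Day 28, with no category change recorded since the last entry, counts as observed in the last recorded category.
2. A Day 28 visit score dated within the protocol's ±5 days is assigned to Day 28, taking the one nearest to Day 28. Death and discharge dates take precedence. A score from Days 29 to 33 is used only if no change is dated after Day 28.
3. Only participants whose status is truly unknown are excluded.

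The first rule should carry most of the weight, because scores from Days 29 to 33 post-date a status that SAP 6.2 defines through Day 28.

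**Cost.** A few lines of text and a small programming change, with no new data collection. If the SAP is already final, its own rule is to document the change in the study report. There are two downsides. Version (2) will match version (1) for continuing inpatients, so the versions will differ at Day 28 only for participants of unknown status. And a score from a nearby day may stand in for Day 28.

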4. SUBJECT DISPOSITION

4.1. Subject Enrollment and Disposition

The number and percentage of participants enrolled at each investigator site will be summarized by group and overall using the Expanded RDV-Treated Analysis Set. The denominator for this calculation will be the number of participants in the Expanded RDV-Treated Analysis Set.

The summary of subject disposition will be provided by group and overall for all screened participants. This summary will include the number of participants screened, screen failure participants who were not enrolled, participants who met all eligibility criteria and were not enrolled, participants enrolled, participants enrolled but never treated, and participants in the Expanded RDV-Treated Analysis Set.

In addition, the number and percentage of the participants in the following categories will be summarized:

- Completed 10-day treatment on study drug as recorded on the Study Drug Completion form
- Prematurely discontinuing study drug prior to completion of 10 days of dosing with summary of reasons for discontinuing study drug as recorded on the Study Drug Completion form
- Completed study
- Prematurely discontinuing from study with summary of reasons for discontinuing study as recorded on the Study Completion form

The denominator for the percentages of participants in each category will be the number of participants in the Expanded RDV-Treated Analysis Set.

A data listing of reasons for study drug/study discontinuation will be provided.

4.2. Extent of Study Drug Exposure

4.2.1. Exposure to Study Drug

Number of doses received will be summarized by group for the Expanded RDV-Treated Analysis Set.

4.3. Protocol Deviations

A listing will be provided for all enrolled participants who violated at least 1 inclusion or exclusion criterion. The listing will include the criteria not met.

Protocol deviations occurring after participants entered the study are documented during routine monitoring. The number and percentage of participants with important protocol deviations by deviation reason and the total number of important protocol deviations by deviation reason (eg, nonadherence to study drug, violation of select inclusion/exclusion criteria) will be summarized by group for the Expanded RDV-Treated Analysis Set. A by-subject listing will be provided for those participants with important protocol deviations.

5. BASELINE CHARACTERISTICS

5.1. Demographics and Baseline Characteristics

Participant demographic data (eg, sex, race/ethnicity, and age) and baseline characteristics (eg, body weight, height, and body mass index [BMI]) will be summarized by group and overall using descriptive statistics (n, mean, SD, median, Q1, Q3, minimum, and maximum) for continuous data and by the number and percentage of participants for categorical data. The summaries of demographic data and baseline participant characteristics will be provided for the Expanded RDV-Treated Analysis Set.

Age group (< 65 and ≥ 65) will be summarized by group and overall.

A by-subject demographic listing will be provided.

5.2. Other Baseline Characteristics

The following baseline disease characteristics will be summarized by group and overall using descriptive statistics:

- Clinical status (7-point ordinal scale)
- Duration of hospitalization prior to first dose of RDV
- Duration of symptoms prior to first dose of RDV
- AST
- ALT
- Oxygen support status based on the 7-point ordinal scale (invasive mechanical ventilation, high flow oxygen, low flow oxygen, room air)
- Region (North America, Europe, Asia)

5.3. Medical History

Any medical condition or clinically significant laboratory abnormality with an onset date before the consent form is signed and not related to a protocol-associated procedure is considered to be preexisting and should be documented as medical history. General medical history data will be collected at screening and coded using the Medical Dictionary for Regulatory Activities (MedDRA). A summary table will present the percentages of participants reporting each medical history preferred term, sorted first in alphabetical order by system organ class (SOC) and then by preferred term (PT) in descending order of total frequency within SOC. Preferred terms with the same total frequency will be sorted in alphabetical order.

6. EFFICACY ANALYSES

6.1. Primary Efficacy Endpoint

The primary efficacy endpoint was analyzed for Part A of the study and is not described in this SAP.

6.2. Efficacy Endpoints of Interest

Efficacy endpoints of interest include endpoints based on clinical status assessed by a 7-point ordinal scale. The endpoint will be derived by combining the available death, hospital discharge alive and ordinal scale assessment reported by the site, where death supersedes discharge alive and discharge alive supersedes the ordinal scale score reported by the site.

Sites were instructed to report the worst ordinal scale category for each day. Therefore, the ordinal scale result on the day the participant was discharged alive does not necessarily reflect Not hospitalized (7). The definition of clinical status based on the 7-point ordinal scale is defined as follows:

- If a participant dies while hospitalized (as recorded on the Death eCRF and Hospitalization eCRF), the endpoint on the day of death and all subsequent days through Day 28 will be set to Death (1)
- If the participant is discharged alive, the endpoint on the day of discharge alive and all subsequent days through Day 28 will be set to Not hospitalized (7)
- If the participant is discharged alive and dies on the same day or a later day (as recorded on the Death eCRF and Hospitalization eCRF), the endpoint on the day of discharge alive and all subsequent days until the day of death will be set to Not hospitalized (7). On the day of death and all subsequent days through Day 28, the endpoint will be set to Death (1),

Every effort will be made to obtain clinical status data for all participants prior to discharge alive. The last known clinical status will be used for days with missing clinical status (eg, where the reason for Hospital Discharge is not “Discharged Alive” and the participant has not died). All post-baseline days with missing ordinal scale score, from Day 2 to Day 14 and Day 28, will use the previous last known clinical status.

Efficacy endpoints of interest include

- Clinical status on Days 1 to 14, Day 28 and last available assessment
- Change in clinical status on Days 5, 7, 11, 14, 28, and last available assessment
- Time to clinical improvement (days): Clinical improvement is defined as a ≥ 2 -point improvement from baseline clinical status or discharged alive on the 7-point ordinal scale using the definition specified above.
- Percentage of participants with a ≥ 2 -point improvement or discharged alive based on the 7-point ordinal scale using the definition specified above on Day 5, Day 7, Day 11, Day 14, Day 28, and last available assessment

- Time to ≥ 1 -point improvement (days) from baseline clinical status on the 7-point ordinal scale using the definition specified above.
- Percentage of participants with a ≥ 1 -point improvement based on the 7-point ordinal scale using the definition specified above on Day 5, Day 7, Day 11, Day 14, Day 28 and last available assessment
- Time to recovery based on the 7-point ordinal scale using the definition above, where recovery is defined as an improvement from a baseline score of 2 through 5 to a score of 6 or 7, or an improvement from a baseline score of 6 to a score of 7
- Percentage of participants with recovery based on the 7-point ordinal scale using the definition specified above on Day 5, Day 7, Day 11, Day 14, Day 28 and last available assessment
- Number of days of oxygen support while hospitalized through discharge alive, death or Day 14 based on the 7-point ordinal scale reported values (See [Appendix 2](#)). This summary will present results separately for participants who died on or prior to Day 14 and those who were discharged alive on or prior to Day 14 and will include:

Days on invasive mechanical ventilation

Days on high flow oxygen devices

Days requiring low flow supplemental oxygen

Because oxygen support status was collected only while the participant was in the hospital, if a participant was discharged alive and died afterwards, the participant will be included only in the summary for participants discharged alive.

- Shift in oxygen support status from baseline to Days 5, 7, 11, 14, 28 and last available assessment
- Duration of hospitalization (days) (duration from hospital admission and duration from Day 1). Duration of hospitalization is calculated through Day 28 for participants who were discharged alive on or prior to Day 28. If participants were rehospitalized for COVID-19 related reasons, the hospitalization discharge information is entered in the eCRF database using the latest hospitalization admission.
- All-cause mortality

